9.1.4 K-SADS-PL Rater Qualification and Certification

The K-SADS-PL should be administered by a rater who has adequate experience with paediatric patients with MDD. The rater should be a psychiatrist or doctor of osteopathy (DO) specialised in child and adolescent psychiatry, or a clinical paediatric (neuro-) psychologist involved in clinical practice.

Any exceptions must be discussed and approved by Lundbeck.

Only raters who have been certified in a study-specific Rater Certification Programme will be authorized to rate in this study. Documentation of training and certification will be delivered to the raters for archiving in the investigator trial master file (TMF). No patient may be rated before the documentation has been delivered.

New raters joining the study will be trained and certified locally using the same certification processes.

9.1.5 Drug and Alcohol Screen

It is not mandatory to screen for drugs and/or alcohol. However, it can be performed at any visit during the open-label and double-blind periods, at the discretion of the investigator. The blood and urine drug screen samples will be analysed at the central laboratory.

9.2 Efficacy Assessments

9.2.1 Clinical Outcome Assessments (COAs)

9.2.1.1 Use of COA Tools

The following clinician-rated electronic assessment tools will be used and accessed via a tablet provided by Signant Health, called a Rater Station:

- CDRS-R – assessing depressive symptoms
- CGI-S/I – assessing clinical global impression

Detailed instructions on how to administer the scales and how to score using the scales will be provided to the site in a *Rater Station Site Manual*.

The CDRS-R will be administered in the local language. Only scales provided by Lundbeck that have been validated in the language to which they have been translated will be used in this study.

9.2.1.2 Children depression rating scale revised version (CDRS-R)

The CDRS-R²⁷ is a clinician-rated scale to measure the severity of depression of children and adolescents. The CDRS-R is rated by a clinician following interviews with the child and parent(s) and consists of 17 items: 14 items rate verbal observations, and 3 items rate nonverbal observations (tempo of language, hypoactivity, and nonverbal expression of depressed affect). Items are rated for severity on a 7-point scale (1 to 7) for 14 items, and on a 5-point scale (1 to 5) for 3 items (sleep disturbance, appetite disturbance, and listless speech). The total score ranges from 17 (normal) to 113 (severe depression). The CDRS-R can be administered by a clinician after a training session. It takes approximately 20 to 30 minutes to administer and rate the CDRS-R.

9.2.1.3 Clinical Global Impression Scales (CGI-S/I)

The CGI²⁸ was developed to provide global measures of the severity of a patient's clinical condition and improvement or worsening during clinical studies.

The clinician will use the scale to assess depressive symptoms.

The CGI consists of two clinician-rated subscales: severity of illness (CGI-S) and global improvement (CGI-I).

The CGI-S provides the clinician's impression of the patient's current state of mental illness. The clinician uses his or her clinical experience of this patient population to rate the severity of the patient's current mental illness on a 7-point scale ranging from 1 (Normal - not at all ill) to 7 (among the most extremely ill patients).

The CGI-I provides the clinician's impression of the patient's improvement (or worsening). The clinician assesses the patient's condition relative to Randomization (as the CGI-I only will be assessed in the Double-blind period) on a 7-point scale ranging from 1 (very much improved) to 7 (very much worse). In all cases, the assessment should be made independent of whether the rater believes the improvement is drug-related or not.

An experienced clinician can use the CGI after a short training session. It takes 1 to 2 minutes to score the CGI after a clinical interview.

9.2.1.4 Rater Qualification

The CDRS-R and CGI-S/I scales should only be administered by a rater who has adequate experience with paediatric patients with MDD and who has adequate experience in rating scales. The rater should be a psychiatrist or DO specialised in child and adolescent psychiatry, or a clinical paediatric (neuro-) psychologist involved in clinical practice.

The CGI-S/I should be administered by the investigator responsible for the patient. The investigator must be a psychiatrist or DO specialised in child and adolescent psychiatry that has adequate experience with paediatric patients with MDD.

Any exceptions must be discussed and approved by Lundbeck.

Only raters who have been certified in a study-specific Rater Certification Programme will be authorized to rate in this study. Documentation of training and certification will be delivered to the raters for archiving in the investigator TMF. No patient may be rated before the documentation has been delivered.

The individual scores from the primary scale rater qualification session will be used to document inter-rater reliability and filed in the sponsor TMF.

New raters joining the study will be trained and certified locally using the same certification processes. Rater training and certification will be conducted by Signant Health.

For each individual patient, the same certified rater should rate the patient. For unforeseen circumstances, certified back-up raters should be available throughout the study.

9.2.2 Patient and/or Parent Reported Outcomes (PROs)

The following electronic PRO will be completed by the patient on the Rater Station:

- PQ-LES-Q²⁹: designed to assess patient's satisfaction with life

9.2.2.1 Paediatric Quality of Life Enjoyment and Satisfaction Questionnaire (PQ-LES-Q)

The PQ-LES-Q²⁹ is a patient-rated scale designed to assess satisfaction with life. It is an adaptation of the Quality of Life Enjoyment and Satisfaction Questionnaire (Q-LES-Q), which is used to measure quality of life in adults. The PQ-LES-Q consist of 15 items, item 1 to 14 assess the degree of satisfaction experienced by patients in various areas of daily functioning and item 15 allows subjects to summarize their experience in a global rating.

Each item is rated on a 5-point scale from 1 (*very poor*) to 5 (*very good*). The total score range of item 1 to 14 is 14 to 70, with higher scores indicating greater satisfaction. It takes 5 to 10 minutes to complete the scale.

The site staff should instruct patients on how to use the Rater Station. On-screen instructions on how to complete the scale will be available in the Rater Station.

9.3 Pharmacokinetic Assessments

Blood samples (1 mL) for IMP analysis will be collected in ethylenediamine tetra acetic acid (EDTA) tubes simultaneously with clinical safety lab samples. The blood sampling and handling procedures are described in the study-specific *Laboratory Specification Manual*.

The blood samples will be analysed for vortioxetine using methods validated in accordance with the EMA Guideline on Bioanalytical Method Validation³⁰ and the FDA Guidance for Industry.³¹

The bioanalysis of Lu AA21004 will be conducted by the contract laboratory PRA Health Sciences on behalf of Department of LC-MS Bioanalysis, H. Lundbeck A/S. A dedicated protocol for the bioanalytical study and a bioanalytical study report will be prepared by the contract laboratory.

9.4 Safety Assessments

9.4.1 Adverse Events

The patients will be asked a non-leading question (for example, “how do you feel?”, “how have you felt since your last visit?”) at each visit, starting at the Screening Visit. AEs (including worsening of concurrent disorders, new disorders, and pregnancies) either observed by the investigator or reported spontaneously by the patient will be recorded, and the investigator will assess the seriousness and the intensity of each AE and its relationship to the IMP. Results from relevant tests and examinations, such as clinical safety laboratory tests, vital signs, and ECGs, or their corresponding conditions will also be recorded as AEs if considered by the investigator to be clinically significant.

See chapter 10 for further information on AEs.

9.4.2 Clinical Safety Laboratory Tests

The clinical safety laboratory tests are listed in [Panel 5](#).

Panel 5 Clinical Safety Laboratory Tests

Haematology	Liver^b	Serology^c
B-haemoglobin B-erythrocyte count B-total leucocyte count B-neutrophils ^a B-eosinophils ^a B-basophils ^a B-lymphocytes ^a B-monocytes ^a B-thrombocyte count	S-total bilirubin S-conjugated bilirubin S-alkaline phosphatase S-alanine aminotransferase S-aspartate aminotransferase S-gamma-glutamyl transferase	S-HBsAg S-anti HCV
Electrolytes^b	Kidney^b	Infection^c
S-sodium S-potassium S-calcium (total)	S-creatinine S-urea nitrogen	S-C-reactive protein
Endocrine and Metabolic^b	Lipids^{b,e}	Urine^d
S-albumin S-estradiol [girls only] S-luteinising hormone [LH] S-follicle-stimulating hormone [FSH] S-prolactin [PROLCTN] S-glucose ^d S-thyroid-stimulating hormone ^c	S-low density lipoprotein S-high density lipoprotein S-triglycerides S-cholesterol (total)	U-protein (dipstick) U-glucose (dipstick) U-blood (dipstick)
		Pregnancy^f
		U-hCG B-hCG (confirmatory for positive urine test only)

B = blood; HBsAg = hepatitis B surface antigen; hCG = human chorionic gonadotropin; HCV = hepatitis C virus; P = plasma; S = serum; U = urine

a Count and % of total leucocytes

b Clinical chemistry

c Performed at the Screening Visit only

d Microscopic examination (leucocytes, erythrocytes, and casts) will be performed only if any of the urine evaluations are abnormal Fasting, when possible

e Fasting, when possible

f Performed at the Screening Visit only. Only for female patients aged ≥ 10 years or female patients at lower age judged by the investigator to be of childbearing potential

Blood samples for the clinical safety laboratory tests will be collected as outlined in [Panel 2](#) and [Panel 3](#).

The blood and urine drug screen samples will be analysed at the central laboratory. Urine drug screen requires an additional tube, but ethanol is part of the urine drug screen panel so will be optional as a check box on the requisition form without a need for another additional tube.

The additional urine samples will be collected and analysed at the site using dipsticks. If the dipstick evaluation is positive or abnormal, further analysis will be performed at the central laboratory.

The investigator must review (initial and date) the results of the clinical safety laboratory tests as soon as possible after receipt of those results. Out-of-range values must be interpreted by the investigator as “not clinically significant” or “clinically significant” with a comment concerning the planned follow-up. Tests for clinically significant out-of-range values must be repeated, or an appropriate clinical follow-up must be arranged by the investigator and documented on the laboratory report, until the value has stabilized or until the value has returned to a clinically acceptable value (regardless of relationship to the IMP). A patient with a value that is out-of-range at the Completion Visit (Week 26 of double-blind period) or Withdrawal Visit and considered clinically significant must be followed in accordance with usual clinical practice for up to 30 days or until the value normalizes or stabilizes or a diagnosis or reasonable explanation has been established. Any out-of-range values followed after the last protocol-specified contact with the patient will be documented in the patient’s medical records.

Any out-of-range clinical safety laboratory test value considered clinically significant by the investigator must be recorded as an AE on an *Adverse Event Form*.

The central laboratory will be notified by the sponsor when the biological samples may be destroyed.

9.4.3 Vital Signs

The investigator may appoint a designee to measure vital signs, provided this is permitted according to local regulations and provided the investigator has trained the designee how to measure vital signs. The investigator must take responsibility for reviewing the findings.

Blood pressure and pulse rate will be measured using a standard digital meter with adequate cuff size after the patient has rested for at least 5 minutes in a supine position. The patient must then be instructed to change from a supine to a standing position in a manner that includes passing through a sitting position before assuming an upright position. Blood pressure and pulse rate will be measured after the patient has been standing for at least 1 minute but no longer than 5 minutes.

Any out-of-range vital sign considered clinically significant by the investigator must be recorded as an AE on an *Adverse Event Form*.

9.4.4 Height and Weight

The patient’s height will be measured, without shoes.

The patients will be weighed wearing light clothing and no shoes. A similar amount of clothing must be worn on each occasion.

Any weight change considered clinically significant by the investigator must be recorded as an AE on an *Adverse Event Form*.

9.4.5 Electrocardiograms (ECGs)

A standard 12-lead ECG will be recorded using digital ECG recording equipment provided to the investigator or, upon agreement, to an external cardiology centre. The ECGs will be transferred digitally to a central ECG laboratory for evaluation, where they will be reviewed by a paediatric cardiologist. The investigator will be provided with the results and a cardiologic interpretation of the ECG from the central ECG laboratory.

The results from the central ECG laboratory will include the RR, PR, QRS, QT, QT_c, and QT_{CF} intervals.

The investigator has the final decision on the interpretation of the ECG results. Any abnormal ECG result or out-of-range ECG parameter value considered clinically significant by the investigator must be recorded as an AE on an *Adverse Event Form*.

9.4.6 Physical and Neurological Examinations

The investigator may appoint a designee to be primarily responsible for performing the physical examinations, provided this is permitted according to local regulations. The investigator must take responsibility for reviewing the findings. Whenever possible, the same individual should perform all the physical examinations.

The physical examination must, at a minimum, include an examination of appearance, extremities, skin, head, neck, eyes, ears, nose, throat, lungs, chest, heart, abdomen, and musculoskeletal system and must be performed by a physician or physician assistant. If there is no physical examination at the Baseline Visit, the examination at the Screening Visit will be considered the baseline physical examination.

The neurological examination must be performed by a physician.

Any abnormal finding or out-of-range value considered clinically significant by the investigator must be recorded as an AE on an *Adverse Event Form*.

9.4.7 Tanner Staging

Tanner staging is a scale for assessing physical development and sexual maturity during onset and progress of puberty.

The scale includes 5 stages of pubertal changes (called Tanner stages) separate for males and for females.

For female the 5 stages of maturation are recognized by assessing pubic hair and breast development. For male the 5 stages of maturation are recognized by assessing pubic hair, growth of penis and testicles. Post-puberty is defined as a Tanner stage = 5 in both of observed criteria.

The evaluation of Tanner stage will be performed by physician or trained nurse - they will be provided with figures depicting the somatic changes and tables describe these changes in words to facilitate the staging.

Tanner staging will be performed in conjunction with the physical examination according to the schedule displayed in [Panel 2](#) and [Panel 3](#).

9.4.8 Menstrual Cycle

The following will be recorded:

- Age of menarche
- The length of the menstrual cycle (number of days from the first day of menstruation to the day before the first day of the next menstrual period)
- Menstrual cycle regularity

9.4.9 General Behaviour Inventory (GBI) 10-Item Mania Scale

The GBI 10-item mania scale³² is a parent- and subject-rated scale designed to screen for manic symptoms in children and adolescents. The ten items are rated on a 4-point scale from 0 (never or hardly ever) to 3 (very often or almost constantly). The total score ranges from 0 to 30, with higher scores indicating greater pathology. It takes approximately 5 minutes to complete the GBI 10-item mania scale.

The parent-rated scale is validated and appropriate for the use in children and adolescents with psychiatric disorders.³³ The subject-rated scale is validated only for patients in the age group 10 to 17 years.³⁴ Therefore, only the parent-rated scale will be used in this study.

The GBI will be administered in the local language. Only scales provided by Lundbeck that have been validated in the language to which they have been translated will be used in this study.

The site staff should instruct patients and parents/caregivers on how to use the Rater Station. On-screen instructions on how to complete the scale will be available in the Rater Station.

9.4.10 Columbia-Suicide Severity Rating Scale (C-SSRS)

The C-SSRS³⁵ is a semi-structured interview developed to systematically assess suicidal ideation and behaviour of patients participating in a clinical study. The C-SSRS has 4 questions addressing suicidal behaviour, 5 questions addressing suicidal ideation, and sub-questions assessing the severity.

Different versions of the scale are available: in this study, the “Baseline Screening” version will be applied at the Screening Visit and the “Since last visit” version will be applied other visits including the C-SSRS.

A version of the C-SSRS specifically developed for the use in children will be applied in the study population of children aged 7 to 11 years.

An experienced clinician can use the C-SSRS after a short training session. It takes approximately 5 minutes to administer and rate the C-SSRS.

The C-SSRS has 5 questions addressing suicidal ideation. If level 4 or 5 has been answered “yes”, a corresponding SAE should be reported.

If the electronic C-SSRS (eC-SSRS) system™ is temporarily unavailable on the Rater Station, a paper version of the C-SSRS (*C-SSRS Fallback Form – Baseline/Screening Version*) should be administered by the investigator. If the eC-SSRS is unavailable at the Screening Visit, the paper version should be used; however, the patient will have to return to the site to complete the eC-SSRS before he or she may be enrolled in the study. When a *C-SSRS Fallback Form* has been used, it must be kept as a source document in the Patient Binder. Data from the *C-SSRS Fallback Form* will not be transcribed in the eCRF.

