11.1 Data Collection

11.1.1 Electronic Case Report Forms (eCRFs)

eCRFs will be used to collect all the data related to the study, except the external data described in section [11.1.5](#).

The eCRFs use third party software (Rave[®]) to capture data via an online system on a computer. When the investigator enters data in the eCRF (ideally during the visit or as soon as possible, <3 days thereafter), the data will be recorded electronically in a central database over encrypted lines, and all entries and modifications to the data will be logged in an audit trail. Access to the system will only be granted after appropriate and documented training. Written instructions for using the system will be provided along with the training.

Electronic signatures will be used where signatures are required on pages and/or visits. Automated data entry checks will be implemented where appropriate; other data will be reviewed and evaluated for accuracy by the sponsor and/or representatives from specify CRO. All entries, corrections, and changes must be made by the investigator or a delegate.

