12.5.1 Columbia-Suicide Severity Rating Scale (C-SSRS) Scores

The C-SSRS was administered:

At screening using *the Baseline Screening version* to capture the baseline result (de novo patients only) and at every scheduled visit thereafter using the *Since last Visit version* to capture the C-SSRS assessments after baseline.

A summary capturing the patients with suicidal ideation, suicidal behaviour

The numbers and percentages of patients with baseline, or post-baseline suicide-related events based on the C-SSRS will be summarized. For the post-baseline assessments, the most severe score ([Panel 5](#)) per patient related to suicidal ideation and/or behaviour will be summarized.

The number and percentage of patients with no suicidal ideation or behaviour will be summarized. Patients in this category are those who:

answered 'no' to all ideation and behaviour questions; that is, answered 'no' to items in [Panel 8](#) related to suicidal ideation and answered 'no' to items related to suicidal behaviour.

Panel 5 C-SSRS Scores

C-SSRS Score	Related to:
Wish to be dead	Suicidal ideation
Non-specific active suicidal thoughts	
Active suicidal ideation with any methods (not plan) without intent to act	
Active suicidal ideation with some intent to act, without specific plan	
Active suicidal ideation with specific plan and intent	
Preparatory acts or behaviour	Suicidal behaviour
Aborted attempt	
Interrupted attempt	
Non-fatal suicide attempt	
Completed suicide (only applicable for the post-baseline assessments)	

The C-SSRS scores will be summarized per study period and by visit based on the APES (Open Label Period) or APRS (Double- blind Period) for patients with at least one post-baseline C-SSRS assessment in the respective period, regardless of whether they had a baseline C-SSRS assessment.

Missing C-SSRS scores will not be imputed.

Positive responses to *non-suicidal self-injurious behaviour* will be summarized separately.

For patients with any post-baseline suicidal behaviour (C-SSRS scores of 6 to 10), listings will be provided including all C-SSRS scores for those patients; C-SSRS scores related to suicidal behaviour will be flagged.

In addition, a listing with (highest) suicidal behaviour in the study or a period based on C-SSRS scores for those patients, and all SAEs related to suicidality, will be prepared.

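### After Screening, a C-SSRS taken on paper uses a form of the wrong version and has no stated route into the safety data

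*Protocol*

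**What the plan says.** The C-SSRS score is a listed safety endpoint (Protocol section 2, Panel 4; SAP section 2, Panel 1).

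**Version.** Protocol 9.4.10 uses the Baseline Screening version at the Screening Visit and says that "the “Since last visit” version will be applied other visits including the C-SSRS". SAP 12.5.1 makes the same assumption for the analysed data: the scale is given "at every scheduled visit thereafter using the *Since last Visit version* to capture the C-SSRS assessments after baseline".

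**Fallback.** If the electronic scale is temporarily unavailable on the Rater Station, Protocol 9.4.10 says that "a paper version of the C-SSRS (*C-SSRS Fallback Form – Baseline/Screening Version*) should be administered by the investigator". The next sentence deals with Screening separately and adds that "the patient will have to return to the site to complete the eC-SSRS before he or she may be enrolled in the study". The completed form is kept in the Patient Binder as a source document, and "Data from the *C-SSRS Fallback Form* will not be transcribed in the eCRF".

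**Analysis.** SAP 12.5.1 summarizes the C-SSRS by period and by visit, takes each patient's most severe post-baseline score, and counts patients with no ideation or behaviour. It summarizes non-suicidal self-injury separately. It also states: "Missing C-SSRS scores will not be imputed". It does not mention fallback forms.

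**The concern.** Section 9.4.10 is inconsistent with itself. One rule fixes the version for on-treatment visits, and the fallback rule names the other version. The ban on transcription then means that, if a site follows the text, a completed suicidality assessment stays in a binder.

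The trial is in children aged 7 to 11, and the key C-SSRS summary is a worst score per patient. With a worst-score summary, a single assessment can decide a patient's category. A child whose only positive answers were given on a paper form could be counted as having no suicidal ideation or behaviour. What is at stake is the completeness of the C-SSRS tables and their agreement with the SAE and withdrawal data.

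**Working it through.** The plan gives no figure to reproduce here. The check follows one paper form from collection to table, then sets a rough scale.

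**1. Is the fallback rule limited to Screening?** The sentence that names the form applies whenever the system is temporarily unavailable. Screening gets its own sentence with its own remedy. So the general sentence covers later visits, where the version named conflicts with the version required.

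**2. Is there any route into the database after Screening?**

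| Route | What the protocol says | Paper C-SSRS after Screening |
|---|---|---|
| eCRF (11.1.1) | "eCRFs will be used to collect all the data related to the study, except the external data described in section" 11.1.5 | Excluded by 9.4.10 |
| Transcription from the Patient Binder (11.1.4.2) | Described for the paper K-SADS-PL; other paper scales are a fallback, with no transcription rule | None stated |
| External transfer (11.1.5) | Electronic data, including eCOA data | None stated for paper |
| Repeat of the electronic scale (9.4.10) | Required at Screening, before enrolment | None stated |

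Nor would the next visit clearly repair the gap. Judged by its name, a Since-last-visit interview starts from the visit at which the paper form was used.

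**3. In which direction can the tables move?**

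- *Worst score per patient.* The maximum over a subset of assessments cannot exceed the maximum over all of them. For a child with at least one other post-baseline assessment in the period, the score falls or stays the same. A child with no other assessment leaves the table, because SAP 12.5.1 requires at least one in the period.
- *By-visit percentage.* SAP 12.2 uses non-missing values as the denominator. With x positive among n assessed (0 < x < n), losing a negative changes x/n to x/(n − 1), which is higher. Losing a positive gives (x − 1)/(n − 1), which is lower.

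**4. What could surface elsewhere?**

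- Ideation levels 4 and 5: an SAE report is called for (9.4.10), and withdrawal from treatment is required (5.5).
- Suicidal behaviour: withdrawal from treatment is required (5.5). Reasons for withdrawal are recorded in the eCRF (8.5).
- Ideation levels 1 to 3 and non-suicidal self-injury: no mandatory second route. Recording as an adverse event depends on the investigator (9.4.1).

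**5. Scale.** Panel 3 schedules the C-SSRS at Visits 9 to 17, which is 9 visits after randomization. With 80 randomized patients (Protocol 16.10), the maximum is 9 × 80 = 720 assessments. The outage rate p is not in the documents, so 1% to 5% is an assumption.

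- Assessments affected, 720 × p: 7.2 at 1%; 36.0 at 5%.
- Chance that a child attending all 9 visits has at least one affected, 1 − (1 − p)^9, if outages are independent between visits: 8.6% at 1%; 37.0% at 5%.

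Relapsing patients leave the study, so 720 is a ceiling. Take the planning relapse rates of 0.42 and 0.69 over 26 weeks with constant hazards, and count the relapse visit. The expected number of visits per child is then the sum of S(t) over t = 0, 1, 2, 4, 6, 10, 14, 18 and 22 weeks, the starts of the nine visit intervals.

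- Vortioxetine, S(t) = 0.58^(t/26): sum 7.61.
- Placebo, S(t) = 0.31^(t/26): sum 6.45.
- Total: 40 × (7.61 + 6.45), about 563, before other dropout. At 1% to 5% that is about 6 to 28 affected.

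The open-label period (Visits 3 to 8, about 150 enrolled) adds at most 6 × 150 = 900 assessments, or 9 to 45 on the same assumption.

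**The case against.** The strongest reply is that the eCRF is not the normal home of C-SSRS data. The scale runs on the Rater Station, and eCOA data are held outside the eCRF by design (11.1.5). A bar on eCRF transcription is therefore not a bar on later entry through the Rater Station. This stands in part. Late entry is neither described nor forbidden, so the supportable statement is that no route is specified. A reader might infer that the data can never be entered, but the text does not go that far.

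A second reply is that the fallback paragraph was meant for Screening only. Its wording is not so limited. If that was the intention, later visits have no named C-SSRS fallback form, and the section still needs correcting.

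Four stronger readings are tempting and are not supported:

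- *Reported incidence always falls.* This is true only of the worst-score count for children with other assessments. By-visit percentages can rise.
- *The treatment comparison is biased.* Nothing suggests that outages would differ by arm.
- *Suicidal children would go undetected.* The interview still takes place, the form is kept as source, and the SAE and withdrawal rules apply. The gap is in the analysed data.
- *The form asks about the wrong period.* The documents name two versions and assign them to visits but do not give the recall period of the Baseline/Screening form. The mismatch of version stands. How far it would mix in earlier events is an assumption.

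**Conclusion.** The point holds as an inconsistency in the protocol and a gap in the data flow. Followed as written, 9.4.10 applies the wrong version on paper after Screening and leaves the result with no stated path into a listed safety endpoint. Confidence in the textual finding is high; confidence in its practical impact is not, because the frequency of outages is unknown.

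The effect is confined mainly to ideation levels 1 to 3 and non-suicidal self-injury in the C-SSRS tables. Its size rests on an assumed outage rate: at 1% to 5%, at most about 7 to 36 of 720 double-blind assessments, or about 6 to 28 once planned relapse withdrawals are allowed for. The primary endpoint is untouched. The correction should be made because it is cheap and the endpoint is suicidality in children.

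**What to change.** In Protocol 9.4.10:

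- Name a paper Since-last-visit form as the fallback for all visits after Screening, and keep the Baseline/Screening form for Screening.
- Replace the sentence that bars transcription with a requirement that the data be entered in the study database and flagged as paper-sourced. An eCRF page or late entry in the eCOA system would serve. Late entry avoids holding the same scale in two sources.

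Both changes are needed: entering data from the wrong version would not make them comparable with the other visits.

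In SAP 12.5.1, state that these records count in the by-period, by-visit and most-severe-score summaries.

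The cost is one extra form, an eCRF page or an eCOA entry procedure, a line in the SAP and a small data-entry burden at sites. No clinical rule changes.
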